4.4 Research Tissue, Blood, and Urine Samples

Mandatory tumor tissue samples are required at baseline and from radical cystectomy.

Mandatory peripheral blood and urine samples will also be collected.

Time points for tissue, blood, and urine samples are outlined in the study parameters (Section 11) and specific requirements are outlined in the correlative section of this protocol (Section 14) and the lab manual.

5. Study Design

This is a Phase Ib open-label clinical trial for patients that are either cisplatin-ineligible or refuse cisplatin-based chemotherapy and have MIBC (T2-T4a, N0-N1, M0). Patients will be sequentially enrolled first into Cohort 1 treated with nivolumab alone (N=12). In the absence of the occurrence of high rate of treatment related AEs as defined in Section 5.4 and 13.1.1 with neoadjuvant nivolumab treatment, the study will proceed with enrollment into Cohort 2 of neoadjuvant treatment with combination nivolumab/lirilumab. (In both cohorts, neoadjuvant treatment must start within 10 weeks of transurethral resection of the most recent TURBT that showed muscularis propria invasion). Each group will receive a total of 4 weeks (week 0 and 4) of neoadjuvant therapy followed by radical cystectomy (RC) with bilateral (standard or extended) pelvic lymph node dissection (PLND).

The RC with bilateral (standard or extended) PLND will occur as soon as possible but within 6 weeks after the last neoadjuvant dose in either cohort.

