5.4 Interim Safety Analysis

After 6 and 12 patients on Cohort 1 and 6 patients on Cohort 2 complete surgery, the study will be monitored for nivolumab or nivolumab/lirilumab treatment-related toxicities as noted below.

- Any Grade hypophysitis, meningitis, or immune-related neurologic AEs

- Grade 2 or higher myocarditis
- Persistent Grade 2 immunologic AEs (such as colitis, pneumonitis, and nephritis) that do not recover to Grade 1 or resolve within 6 weeks after the last dose of study drug (Exceptions: rash, fatigue, amylase/lipase elevations, other electrolyte abnormalities).
- Grade 3 or higher immunologic AEs such as uveitis, pericarditis, hepatitis, colitis/diarrhea, nephritis, pancreatitis, myositis, endocrine, rash, etc., except Grade 3 hypothyroidism or Grade 3 infusion reaction.
- Grade 4 non immunologic AEs, as well as Grade 4 hypothyroidism or Grade 4 infusion reaction.

There will be no suspension to accrual after the first 6 patients in each cohort. Also, accrual will start on Cohort 2 once accrual to Cohort 1 is complete (unless needed based on toxicity noted).

If 3 or more of these 6 patients on a single cohort experience nivolumab or nivolumab/lirilumab treatment-related adverse events as noted above, the study will be suspended for a safety review.

6. Treatment Plan

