13.1.1 Interim Safety Analysis (Primary Endpoint)

Treatment-related toxicities as noted below related to nivolumab or nivolumab/lirilumab will be monitored in each cohort of the study separately after 6 and 12 patients in Cohort 1 and 6 patients in Cohort 2 have completed surgery. There will be no suspension to accrual.

- Any Grade hypophysitis, meningitis, or immune-related neurologic AEs
- Grade 2 or higher myocarditis
- Persistent Grade 2 immunologic AEs (such as colitis, pneumonitis, and nephritis) that do not recover to Grade 1 or resolve within 6 weeks after the last dose of study drug (Exceptions: rash, fatigue, amylase/lipase elevations, other electrolyte abnormalities).
- Grade 3 or higher immunologic AEs such as uveitis, pericarditis, hepatitis, colitis/diarrhea, nephritis, pancreatitis, myositis, endocrine, rash, etc., except for Grade 3 hypothyroidism, Grade 3 pruritus or Grade 3 infusion reaction.
- Grade 4 non immunologic AEs, as well as Grade 4 hypothyroidism or Grade 4 infusion reaction.

If 3 or more of these 6 patients on a single cohort experience treatment-related adverse events as noted above related to nivolumab or nivolumab/lirilumab, the study will be suspended for a safety review. The following table gives the probabilities of stopping given various probabilities of toxicity.

True but unknown probability of immunologic toxicity	0.17	0.25	0.33	0.42	0.5
Probability of suspension	0.06	0.17	0.32	0.49	0.66

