#### **7.8. Interim Analysis**

There will be 3 interim safety analyses in this study. After 6 and 12 patients on Cohort 1 and 6 patients on Cohort 2 complete surgery, the study will be monitored for nivolumab or nivolumab/lirilumab treatment-related toxicities as noted below.

- Any Grade hypophysitis, meningitis, or immune-related neurologic AEs
- Grade 2 or higher myocarditis
- Persistent Grade 2 immunologic AEs (such as colitis, pneumonitis, and nephritis) that do not recover to Grade 1 or resolve within 6 weeks after the last dose of study drug (Exceptions: rash, fatigue, amylase/lipase elevations, other electrolyte abnormalities).
- Grade 3 or higher immunologic AEs such as uveitis, pericarditis, hepatitis, colitis/diarrhea, nephritis, pancreatitis, myositis, endocrine, rash, etc., except Grade 3 hypothyroidism or Grade 3 infusion reaction.
- Grade 4 non immunologic AEs, as well as Grade 4 hypothyroidism or Grade 4 infusion reaction.

The first interim safety analysis will be performed as soon as the 6th patient in cohort 1 complete radical cystectomy (RC) surgery. A treatment-related AE by toxicity grade and SOC summary tables will be provided to clinical team review to determine whether 3 or more patients meet above specified AEs. If 3 or more patients are identified, the study will be suspended for a safety review.

An AE listing will also be provided for clinical team review.

The 2nd interim safety analysis will be performed as soon as the 12th patient in cohort 1 complete RC surgery. The same AE analysis as the first interim analysis will be performed for the all 12 patients. If 6 or more patients experience above specified AEs, the study will be suspended for a safety review.

The 3rd interim safety analysis will be performed as soon as the 6th patient in cohort 2 complete RC surgery. The same AE analysis will be repeated for the all 18 patients. If 9 or more patients experience above specified AEs, the study will be suspended for a safety review.

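### Each safety look follows at once on a surgery due within 6 weeks of the last dose, so for the newest patients the 6-week persistent Grade 2 criterion is still open and the suspension count can miss events

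*Protocol*

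**What the plan says.** Protocol 5.4 ties the looks to surgery: "After 6 and 12 patients on Cohort 1 and 6 patients on Cohort 2 complete surgery, the study will be monitored". Protocol 13.1.1 repeats the trigger and, for the combination cohort, waits until "6 patients in Cohort 2 have completed surgery". Neither section gives a data cut-off or a minimum follow-up. The immediacy comes from SAP 7.8: "The first interim safety analysis will be performed as soon as the" sixth Cohort 1 patient finishes cystectomy. The SAP words the second and third looks in the same way.

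Five kinds of treatment-related event count. One is a persistent Grade 2 immunologic event, defined as one "that do not recover to Grade 1 or resolve within 6 weeks after the last dose of study drug". Protocol Section 5 (Study Design) times the operation inside the same interval: it "will occur as soon as possible but within 6 weeks after the last neoadjuvant dose in either cohort".

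The thresholds differ between the documents. The protocol's rule begins "If 3 or more of these 6 patients on a single cohort experience". SAP 7.8 uses 3 at the first look. At the second, on all 12 Cohort 1 patients: "If 6 or more patients experience above specified AEs, the study will be suspended for a safety review". At the third it pools all 18 patients and requires 9.

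Accrual does not pause for the looks (5.4, 13.1.1). Adverse events are followed for 100 days after neoadjuvant treatment (5.3, 8.2).

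**The concern.** The patient whose operation triggers a look has, on schedule, reached at most 6 weeks after the last dose, and less if surgery is done promptly as asked. Patients dosed shortly before may be in the same position. For all of them, a Grade 2 colitis, pneumonitis or nephritis that is still ongoing has neither met nor failed the criterion. I found no rule for this case in 5.4, 13.1.1 or SAP 7.8, and the missing-data rules in SAP 7.3 do not cover it.

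Taken literally, the definition lets such an event be added later but never removed, so any error runs towards not suspending. Cohort 2 matters most. It is the new combination, it has one look after 6 of 24 patients, and dosing continues meanwhile. Late events are still collected, but nothing sends them back to the rule.

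**Working it through.** **1. The plan's own figures.** The 13.1.1 table is the binomial tail P(X ≥ 3), X ~ Bin(6, p). At p = 1/3 it is 1 − (64 + 192 + 240)/729 = 233/729 = 0.320. At p = 1/6, 1/4, 1/3, 5/12 and 1/2 it is 0.062, 0.169, 0.320, 0.490 and 0.656. The table prints 0.06, 0.17, 0.32, 0.49 and 0.66, so it is reproduced. It treats every one of the six patients as assessable on all five criteria.

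**2. How many patients are pending at a look.** Inputs from the documents: 2-3 patients a month (Protocol 5.1) and a 42-day criterion. Assumptions: evenly spaced accrual, and surgery s weeks after the last dose for everyone. The gap between patients is g = 30.4/2 = 15.2 or 30.4/3 = 10.1 days. The patient k places before the triggering one is 7s + k·g days past the last dose. Count those under 42 days:

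| Surgery at week | 2 per month | 3 per month |
|---|---|---|
| 2 | 2 | 3 |
| 3 | 2 | 3 |
| 4 | 1 | 2 |
| 5 | 1 | 1 |
| 6 | 0 | 0 |

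With random (Poisson) arrivals the mean runs from 1.5 (2 per month, week 5) to 3.7 (3 per month, week 2).

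**3. Effect on the protocol's 3-of-6 rule.** Let m patients be pending and let f be the share of qualifying toxicity that is persistent Grade 2 only. The documents do not give f, so a range is used. A pending patient is counted with probability p(1 − f), any other with p:

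P(suspend) = P(A + B ≥ 3), A ~ Bin(6 − m, p), B ~ Bin(m, p(1 − f)).

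Example: p = 1/3, f = 1/3, m = 2, so a pending patient has 2/9. A is 0 to 4 with probabilities (16, 32, 24, 8, 1)/81. B is 0 to 2 with (49, 28, 4)/81. Then P = 9/81 + (24 × 32 + 32 × 4)/6561 = 1625/6561 = 0.248.

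| True rate | f | m = 0 | m = 1 | m = 2 | m = 3 |
|---|---|---|---|---|---|
| 1/3 | 10% | 0.320 | 0.309 | 0.298 | 0.287 |
| 1/3 | one third | 0.320 | 0.283 | 0.248 | 0.214 |
| 1/3 | half | 0.320 | 0.265 | 0.213 | 0.165 |
| 1/2 | 10% | 0.656 | 0.641 | 0.625 | 0.608 |
| 1/2 | one third | 0.656 | 0.604 | 0.549 | 0.491 |
| 1/2 | half | 0.656 | 0.578 | 0.492 | 0.402 |

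**4. Effect on the SAP's third look.** With 9 of 18 pooled, p = 1/3 and f = one third, the probability is 0.108 with nobody pending and 0.097, 0.087 and 0.078 with 1, 2 and 3 pending. The figures in step 3 therefore describe the protocol's rule, not this one. The two rules are themselves far apart at p = 1/3: 0.320 against 0.108.

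**The case against.** Much of the case on the other side stands.

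- **Scope.** A reader might infer that persistent Grade 2 events cannot be counted at all at a look. The documents do not support that. Patients treated earlier have passed 6 weeks, the other four criteria do not use this clock, and surgery at week 6 leaves almost no gap. An operation delayed beyond week 6, perhaps by toxicity, leaves none for that patient.
- **Convention.** A reader might also infer that a pending event is scored as no event. No passage says so. SAP 7.8 gives the clinical team tables by grade and an event listing, so ongoing Grade 2 events should be visible. The gap is a missing rule, which allows an undercount but does not prove one.
- **Later looks.** Cohort 1 events that mature late can re-enter at the SAP's 12- and 18-patient looks, although against thresholds of 6 and 9. This does not help the six Cohort 2 patients, for whom no look follows.
- **Size.** Surgery timing and the persistent Grade 2 share are both assumed. At a 10% share the loss at p = 1/3 is only 1 to 3 points.
- **Consequence.** The rule triggers a review, not termination. The primary endpoint concerns Grade 3 or higher events, so its estimate is unaffected.

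**Conclusion.** The point holds as a gap in the suspension rule. On schedule, a look run under SAP 7.8 comes at or before the 6-week mark for the triggering patient. About 1-3 of the 6 patients are then not yet assessable on one of five criteria, rather more if accrual is 3 a month with surgery at week 2, and almost none if surgery is at week 6. The count can miss events, and the 13.1.1 table then overstates the chance of suspension.

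Under the protocol's rule at a true rate of 1/3, the loss with 1-3 pending patients is 1 to 3 points if the share is 10%, 4 to 11 if one third, and 5 to 15 if half. These figures rest on the assumed share and surgery timing. The exposure is greatest at the single Cohort 2 look, where the protocol and SAP thresholds also disagree. Severity: should-fix.

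**What to change.** In Protocol 5.4, Protocol 13.1.1 and SAP 7.8:

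1. Run each look when planned, and flag every treatment-related Grade 2 immunologic event still ongoing at the data cut as pending, subject to the exceptions already listed.
2. Re-tabulate against the same threshold once every patient in that look has reached 6 weeks after the last dose. This matters above all for Cohort 2.
3. Reconcile the protocol's single-cohort rule of 3 of 6 with the SAP's pooled rule of 9 of 18 at the third look, and give operating characteristics for the rule that will apply. SAP 2.1 says that it supersedes the protocol's statistical considerations and will identify substantial differences, yet SAP 8 reports no changes.

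Counting pending events provisionally at the first tabulation is optional. It raises the chance of a review above the table, because some of those events will resolve in time; if it is adopted, say so beside the table.

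The cost is a few sentences and one repeat adverse event listing per look. No look is delayed, and items 1 and 2 change no threshold and no treatment rule.

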6.1 Overview

No investigational or commercial agents or therapies other than those described below may be administered with the intent to treat the subject's malignancy.

Neoadjuvant treatment must start within 10 weeks of transurethral resection of the most recent bladder tumor (TURBT) that showed muscularis propria invasion.

Patients enrolled in the trial will be administered one of two of the following treatment regimens:

Cohort 1: Nivolumab 480 mg IV over approximately 30 minutes every 4 weeks for 2 neo-adjuvant doses (week 0 and 4) followed by radical cystectomy (RC) with bilateral (standard or extended) pelvic lymph node dissection (PLND) as soon as possible but within 6 weeks after the last neoadjuvant infusion.

Cohort 2: Nivolumab 480 mg intravenously (IV) over approximately 60 minutes every 4 weeks for 2 neo-adjuvant doses (week 0 and 4) with at least a 30 minute rest between infusions followed by lirilumab 240 mg IV over approximately 60 minutes every 4 weeks for 2 neo-adjuvant doses (week 0 and 4) followed by RC with bilateral (standard or extended) PLND as soon as possible but within 6 weeks after the last neoadjuvant infusion.

NOTE: A few mild infusion reactions occurred on Cohort 2 with the nivolumab infusion, requiring only steroids and resuming dose at 50%. Infusion time increased to 60 minutes per package insert guidelines.

6.1.1 Nivolumab Administration

Cohort 1

Neoadjuvant Dose: Subjects will receive nivolumab 480 mg IV over approximately 30 minutes for a total of 2 doses on week 0 and 4.

Nivolumab is to be administered as an approximately 30 minute IV infusion, using a volumetric pump with a 0.2/0.22 micron in-line filter. It is not to be administered as an IV push or bolus injection. Nivolumab infusion will be followed by at least a 30 minute rest before lirilumab infusion is given.

Cohort 2

Neoadjuvant Dose: Subjects will receive nivolumab 480 mg IV over approximately 60 minutes for a total of 2 doses on week 0 and 4.

Nivolumab is to be administered as an approximately 60 minute IV infusion, using a volumetric pump with a 0.2/0.22 micron in-line filter. It is not to be administered as an IV push or bolus injection. Nivolumab infusion will be followed by at least a 30 minute rest before lirilumab infusion is given.

Refer to Section 12 for further handling and stability information.

6.1.2 Lirilumab Administration

Cohort 1

Subjects will not receive lirilumab.

Cohort 2

Neoadjuvant Dose: Subjects will receive lirilumab 240mg IV over 60 approximately minutes for a total of 2 doses on week 0 and 4.

Lirilumab is to be administered as an approximately 60 minute IV infusion, using a volumetric pump through a non-di-2-ethylhexyl phthalate (DEHP) or DEHP IV infusion set with a 0.2-micron polyethersulfone in-line filter. It is not to be administered as an IV push or bolus injection.

Refer to Section 12 for further handling and stability information.

6.1.3 Name of Other Modality or Procedures

All patients enrolled in this trial will undergo a RC with bilateral (standard or extended) PLND as soon as possible but within 6 weeks of the last dose of neoadjuvant therapy as outlined above.

7. Dose Delays

All toxicities should be graded according to the National Cancer Institute (NCI) Common Terminology Criteria for Adverse Events Version 5.0 (CTCAE V5.0). A copy of the CTCAE V5.0 can be downloaded from the CTEP website (<http://www.ctep.cancer.gov>).

A +/-3 day window is allowed for scheduled therapy, required tests and/or visits except as otherwise noted. Delays due to holidays, weekends, bad weather or other unforeseen circumstances will be permitted.

Dose delays are not required for adverse events not deemed to be related to study treatment (i.e. events due to underlying disease) or for laboratory abnormalities not deemed to be clinically significant. Treat accordingly per institutional standards.

Any patient who cannot receive study therapy within 6 weeks from the previous dose in either cohort, will be permanently discontinued, except as noted below.

NO dose modifications will be allowed.

7.1 Dose Delays for Treatment Related Hematological Toxicity

7.1.1 Grade 1 and Grade 2 Toxicities

No dose interruptions will be performed for Grade 1 or 2 hematologic toxicities.

7.1.2 Grade 3 Toxicities

Study therapy will be permanently discontinued for Grade 3 drug-related thrombocytopenia >7 days or associated with bleeding.

If the patient experiences other Grade 3 treatment related hematologic toxicity in either study cohort, all study therapy must be withheld until the toxicity has resolved to ≤ Grade 1. If the Grade 3 toxicity does not resolve to ≤ Grade 1 within 21 days, all study therapy will be **permanently discontinued**.

7.1.3 Grade 4 Toxicities

If the patient experiences Grade 4 treatment related hematologic toxicity in either study cohort, all study therapy must be **permanently discontinued** regardless of the time to resolution ≤ Grade 1.

7.2 Dose Delays for Treatment Related Non-Hematological Toxicity

See Appendix III for Management Algorithms for Endocrinopathy, Gastrointestinal, Hepatic, Neurological, Pulmonary, Renal, and Skin Adverse Events.

7.2.1 Grade 1 and Grade 2 Toxicities

No dose interruptions will be performed for Grade 1 or 2 non-hematologic toxicities, except for:

- Any grade hypophysitis, meningitis, immune-related neurological AEs
- Any Grade 2 drug-related uveitis, eye pain, or blurred vision that does not respond to topical therapy and does not improve to Grade 1 severity within the retreatment period OR requires systemic treatment will require permanent discontinuation.
- Colitis (Grade 2)
- AST, ALT, bilirubin (Grade 2)
- Pneumonitis (Grade 2)
- Nephritis (Grade 2)

- Infusion reaction that does not resolve within an hour of stopping infusion (Section 7.3 for Infusion Reaction Guidelines), or
- Other intolerable or persistent Grade 2 drug-related AE, as per physician discretion.

Discontinue treatment for persistent Grade 2 immunologic AEs (such as colitis, pneumonitis, and nephritis) that do not recover to Grade 1 or resolve within 6 weeks after the last dose of study drug (Exceptions: rash, fatigue, amylase/lipase elevations, other electrolyte abnormalities).

In addition, discontinue treatment for persistent Grade 2 ALT, AST, or bilirubin that do not recover to Grade 1 or resolve within 6 weeks after the last dose of study drug. A thorough investigation of the cause of the ALT, AST, or total bilirubin elevation is recommended including the exclusion of other causes – e.g. concurrent medications, infection, injury, hypo-perfusion, and alcohol consumption. Close monitoring of hepatic labs at least weekly and consideration of imaging such as ultrasound of the liver is suggested.

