7.2.2 Grade 3 Toxicities

Subjects will be required to permanently discontinue all study drugs for the following AEs:

- Any Grade 3 non-skin, drug-related AE lasting >7 days or recurs, with the following clarifications:
 - Grade 3 drug-related uveitis, pneumonitis, myocarditis, bronchospasm, hypersensitivity reaction, or infusion reaction of any duration requires discontinuation.
 - Grade 3 drug-related endocrinopathies, adequately controlled with only physiologic hormone replacement, do not require discontinuation. Adrenal insufficiency requires discontinuation regardless of control with hormone replacement.
 - Grade 3 drug-related laboratory abnormalities do not require treatment discontinuation except:
 - Grade ≥ 3 drug-related AST, ALT, or total bilirubin
 - Concurrent AST or ALT $>3x$ ULN and total bilirubin $>2x$ ULN

For any other Grade 3 treatment related non-hematologic toxicities, if the Grade 3 toxicity does not resolve to \leq Grade 1 within 21 days, all study therapy will be **permanently discontinued**.

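### Grade 2 myocarditis counts towards the safety suspension rule but is not a named reason to hold a dose in section 7.2.1, so withholding dose 2 rests on physician judgement

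*Protocol*

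**What the plan says.** Protocol section 7.2.1 opens with "No dose interruptions will be performed for Grade 1 or 2 non-hematologic toxicities, except for" and then lists the exceptions. The first is "Any grade hypophysitis, meningitis, immune-related neurological AEs". The others are:

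- certain Grade 2 eye events
- Grade 2 colitis
- Grade 2 AST, ALT or bilirubin elevation
- Grade 2 pneumonitis
- Grade 2 nephritis
- infusion reactions that do not resolve within an hour
- a catch-all, "Other intolerable or persistent Grade 2 drug-related AE, as per physician discretion"

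The same section orders discontinuation for persistent Grade 2 immunologic events "that do not recover to Grade 1 or resolve within 6 weeks after the last dose of study drug".

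Myocarditis first appears in the dosing rules in section 7.2.2: "Grade 3 drug-related uveitis, pneumonitis, myocarditis, bronchospasm, hypersensitivity reaction, or infusion reaction of any duration requires discontinuation". For management, section 7.2 refers the reader on: "See Appendix III for Management Algorithms for Endocrinopathy, Gastrointestinal, Hepatic, Neurological, Pulmonary, Renal, and Skin Adverse Events".

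The suspension rule (Protocol sections 5.4 and 13.1.1, SAP section 7.8) counts treatment-related myocarditis from Grade 2 upwards with no persistence condition. It counts Grade 2 colitis, pneumonitis and nephritis only if they are unresolved six weeks after the last dose. The tally is made once 6 and 12 Cohort 1 patients and 6 Cohort 2 patients have completed surgery. Under the protocol, 3 or more affected patients out of 6 in a cohort trigger suspension.

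**The concern.** The suspension rule treats Grade 2 myocarditis as serious from onset, but the dosing rule for the individual patient does not name it. Because section 7.2.1 forbids interruption by default, what appears on its exception list matters. Read literally, a recent and tolerated Grade 2 myocarditis is neither intolerable nor persistent, so it falls back under the no-interruption default.

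The patient at risk is one who develops treatment-related Grade 2 myocarditis after dose 1 and is due dose 2. The suspension rule cannot protect that patient, because it is tallied after surgery and a single case triggers nothing. What is at stake is patient safety only.

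**Working it through.** **Comparing the lists.** These are the events that the suspension rule counts below Grade 3 without a persistence condition.

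| Event | Counted from | Named exception in 7.2.1 |
|---|---|---|
| Hypophysitis | any grade | yes, any grade |
| Meningitis | any grade | yes, any grade |
| Immune-related neurologic events | any grade | yes, any grade |
| Myocarditis | Grade 2 | no; first named at Grade 3 in 7.2.2 |

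Grade 2 colitis, pneumonitis and nephritis, which the suspension rule counts only if persistent, are also named in 7.2.1. None of the seven classes that section 7.2 lists for Appendix III (endocrine, gastrointestinal, hepatic, neurological, pulmonary, renal, skin) is cardiac.

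**Timing.** Section 6.1 gives doses at weeks 0 and 4. Section 7 says "A +/-3 day window is allowed for scheduled therapy, required tests and/or visits except as otherwise noted". With dose 1 on day 0:

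- Dose 2 falls on day 28 ± 3, that is, day 25 to day 31.
- The persistence rule in 7.2.1 closes at 6 × 7 = day 42.
- The interval from dose 2 to that limit is 42 − 31 = 11, 42 − 28 = 14 or 42 − 25 = 17 days.

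The mandatory stop therefore cannot govern an on-schedule dose 2. The remaining routes are the 7.2.1 catch-all and the general stopping provisions in 8.1 and 8.3, and all of these rest on judgement.

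**The plan's own figures, for context.** Section 13.1.1 prints suspension probabilities of 0.06, 0.17, 0.32, 0.49 and 0.66 at true toxicity rates of 0.17, 0.25, 0.33, 0.42 and 0.5. The exact binomial P(X ≥ 3), n = 6, gives 0.066, 0.169, 0.313, 0.497 and 0.656 at the printed rates. At 2/12, 3/12, 4/12, 5/12 and 6/12 it gives 0.062, 0.169, 0.320, 0.490 and 0.656, which match the table to two decimals. A named hold would not change this table.

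**Size.** Notes in sections 6.1 and 12.1.5 show that Cohort 1 dosing is finished and Cohort 2 has started. A change can reach only Cohort 2 patients not yet given dose 2, at most 24. The documents give no incidence, so the rate p of Grade 2 myocarditis between the two doses is assumed. The chance of at least one case in n patients is 1 − (1 − p)ⁿ.

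| Assumed p | Expected cases, 24p | n = 24 | n = 12 |
|---|---|---|---|
| 0.1% | 0.024 | 2.4% | 1.2% |
| 0.5% | 0.12 | 11.3% | 5.8% |
| 1% | 0.24 | 21.4% | 11.4% |
| 2% | 0.48 | 38.4% | 21.5% |

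These are chances of occurrence. If a share r of cases were re-dosed (also assumed), the chance of at least one re-dosed case in 24 is 1 − (1 − pr)²⁴:

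- p = 0.1%, r = 10%: 0.2%
- p = 1%, r = 10%: 2.4%
- p = 1%, r = 50%: 11.3%
- p = 2%, r = 50%: 21.4%

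**The case against.** The strongest reply is that nothing compels re-dosing. Section 8.1 allows treatment to stop for toxicity that the patient or investigator finds unacceptable, and directs that it should stop if the protocol's constraints harm the patient. Section 8.3 allows removal for unacceptable adverse events or by investigator decision. An event meeting the serious adverse event definition must reach the sponsor within 24 hours. That is all true, and most physicians would probably hold the dose. But the stopping routes are judgements, and reporting follows the event. The same reasoning would apply to Grade 2 pneumonitis and nephritis, which the protocol still names.

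A second reply is that the 7.2.1 list only lifts a prohibition: most of its bullets do not order a hold or give resumption criteria. The wording is indeed thin. Still, only the last bullet is expressly left to physician discretion, so the others read naturally as events for which dosing is interrupted. The absence of a resumption criterion stands as a limit on what one bullet can achieve.

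Third, the suspension rule monitors a cohort and 7.2.1 governs individuals, so the lists need not match. They differ elsewhere, for example on controlled Grade 3 endocrinopathies. This is right, and the point concerns the missing named hold alone.

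Finally, the Appendix III figures are not shown and the investigator's brochures were not available, so the finding applies only to the visible text. The size figures depend wholly on assumed rates.

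**Conclusion.** The concern holds and is minor. In the visible text, a patient with treatment-related Grade 2 myocarditis before dose 2 has only discretionary routes to a hold, whereas the other three events counted below Grade 3 without persistence have a named one. The pattern suggests an omission, and no rationale is given.

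The gap is confined to myocarditis arising between the two doses in at most 24 patients. The occurrence and re-dosing ranges above show what chosen inputs imply; they are not estimates. No endpoint, sample size or operating characteristic changes.

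**What to change.** Add Grade 2 myocarditis as a bullet among the section 7.2.1 exceptions, so that all study drug is held at onset. Keep the existing limit in section 7: "Any patient who cannot receive study therapy within 6 weeks from the previous dose in either cohort, will be permanently discontinued". That leaves the 11 to 17 days after the scheduled dose 2 in which to decide on resumption, handled as for the other Grade 2 holds already listed.

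The cost is one line in an amendment, with no new assessment, data item or patient. The downside is that an affected patient may miss the second of two neoadjuvant doses.
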